5.2. Method of Assignment to Treatment

At entry into Study JAHN, patients who meet all criteria for enrollment will be randomized or assigned treatment by a computer-generated random sequence using an interactive web-response system (IWRS). Patients originally assigned to placebo, 1-mg baricitinib, or 2-mg baricitinib in Studies JAHL or JAHM, or patients originally assigned to placebo or 2-mg baricitinib in Study JAIY and classified as nonresponders, will be randomized in a 1:1 ratio to 2-mg baricitinib or 4-mg baricitinib and will be stratified by disease severity at baseline of JAHN (IGA 0, 1, 2 versus IGA 3 versus IGA 4). All other patients will be assigned to treatment in Study JAHN matching their prior assignment from Studies JAHL, JAHM, or JAIY.

Additional addendum patients will be permitted to enroll directly into Study JAHN on baricitinib 2 mg. These patients will not be blinded to treatment.

At Week 52, patients eligible for the withdrawal and downtitration substudy will be assigned to treatment by a computer-generated random sequence using an IWRS. Rerandomization will follow a 1:1:1 ratio allocation and will be stratified by disease severity (IGA 0, 1 versus IGA 2). Patients entering the substudy on baricitinib 4 mg will be rerandomized to baricitinib 4 mg, baricitinib 2 mg, and placebo; patients entering the substudy on baricitinib 2 mg will be rerandomized to baricitinib 2 mg, baricitinib 1 mg, and placebo.

The IWRS will be used to assign blister packs, each containing double-blind IP tablets, to each patient, starting at Visit 1 (Week 0), and at each visit up to and including Visit 21 (Week 184). Site personnel will confirm that they have located the correct blister packs by entering a confirmation number found on the blister packs into the IWRS.

This study will be conducted internationally in multiple sites. [Table JAHN.5.1](#) describes how regions were defined for stratification in the originating studies.

Table JAHN.5.1. Geographic Regions for Stratification

Region	Country
Europe	Austria, Czech Republic, Denmark, France, Germany, Hungary, Italy, Poland, Spain, Switzerland
Japan	Japan
Rest of World	Argentina, Australia, India, Israel, Korea, Mexico, Russia, Taiwan

6. A Priori Statistical Methods

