6.2. General Considerations

This plan describes *a priori* statistical analyses for efficacy, health outcomes, and safety that will be performed.

Statistical analysis of this study will be the responsibility of Eli Lilly and Company (Lilly). The statistical analyses will be performed using SAS® Version 9.4 or higher.

Not all displays described in this statistical analysis plan (SAP) will necessarily be included in the clinical study report (CSR). Not all displays will necessarily be created as a “static” display. Some may be incorporated into interactive display tools instead of or in addition to a static display. Any display described in this SAP and not included in the CSR would be available upon request.

Statistical tests of treatment effects and confidence intervals (CIs) will be performed at a 2-sided significance level of 0.05, unless otherwise stated.

Data collected at early termination visits will be mapped to the closest scheduled visit if it falls within the visit window as discussed in Section 6.2.2. For by-visit summaries, only visits in which a measure was scheduled to be collected will be summarized. Any unscheduled visit data will be included at the patient-level listings. However, the data will still be used in other analyses, including categorical analyses for safety.

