6.2.3. Analysis Methods

As few placebo patients are expected to be responders, no formal comparisons between treatment groups and placebo will be conducted for the responder and partial responder mITT populations. For the nonresponder mITT population, the following comparisons will be made for Period 1:

- for patients from originating monotherapy studies:
 - baricitinib 2 mg to baricitinib 4 mg versus baricitinib 2 mg to baricitinib 2 mg
 - baricitinib 1 mg to baricitinib 4 mg versus baricitinib 1 mg to baricitinib 2 mg
 - placebo to baricitinib 4 mg versus placebo to baricitinib 2 mg
- for patients from originating combination therapy study:
 - baricitinib 2 mg to baricitinib 4 mg versus baricitinib 2 mg to baricitinib 2 mg
 - placebo to baricitinib 4 mg versus placebo to baricitinib 2 mg

For the Period 2 substudy, the following treatment comparisons will be performed:

- for patients on baricitinib 4 mg in Period 1:
 - placebo versus baricitinib 4 mg
 - baricitinib 2 mg versus baricitinib 4 mg
- for patients on baricitinib 2 mg in Period 1:
 - placebo versus baricitinib 2 mg
 - baricitinib 1 mg versus baricitinib 2 mg

For Period 1, the main analysis method of categorical efficacy variables will use a logistic regression analysis with region, baseline disease severity from originating study (IGA 3 or IGA 4), baseline value from originating study, and treatment group in the model. For Period 2, the main analysis method of categorical efficacy variables will use a logistic regression analysis but with region, baseline disease severity at Week 52, baseline value at Week 52, and treatment

group in the model. In this case, the baseline disease severity at Week 52 can take values in 1 of 2 levels: 1) IGA of 0 or 1, and 2) IGA of 2. Firth's correction will be used in order to accommodate (potential) sparse response rates. The p-value for the odds ratio from the logistic regression model will be used for statistical inference, unless Firth's correction still results in quasi-separation. In that case, a Fisher's exact test p-value will be used for statistical inference. The difference in percentages and 100(1-alpha)% CI of the difference in percentages using the Newcombe-Wilson method without continuity correction will be reported.

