Patients on baricitinib 2 mg or baricitinib 4 mg who are considered nonresponders (IGA >2) at entry into Study JAHN may respond with continued baricitinib treatment. Time to first response (IGA of ≤ 1) will be assessed using cumulative incidence functions for patients remaining on the same dose from the originating study. This will be used to determine when continued baricitinib treatment is futile. Missing IGA data will be replaced using the NRI rule.

For the US submission DBL (data cut-off 13Dec2019), all patients originating from Studies JAHL or JAHM are expected to have either reached the Week 52 visit or have discontinued from the study. Fisher's exact test will be used to test for differences between each baricitinib dose (including those that are randomized to a different dose) and placebo in proportions of patients

experiencing AEs) discontinuation from study drug, and for other categorical safety data. Continuous vital signs, body weight, and other continuous safety variables, including laboratory variables will be analyzed by an ANCOVA with treatment group and baseline value in the model. The significance of within-treatment-group changes from baseline will be evaluated by testing whether or not the treatment group LSM changes from baseline are different from zero; the standard error for the LSM change will also be displayed. Differences in LSM will be displayed, with the p-value associated with the LSM comparison to placebo or appropriate comparator and a 95% CI on the LSM difference also provided. In addition to the LSMs for each group, the within-group p-value for the change from baseline will be displayed.

6.2.4. *Derived Data*

- age (year), derived using first dose date as the reference start date and July 1st of birth year and truncated to a whole-year (integer) age. Patients whose derived age is <18 will have the required minimum age of 18 at informed consent confirmed; reporting for age, age groups, and lab ranges, however, will be based on their derived age.
- age group (<65, ≥65 years old)
- age group (<65, ≥65 to <75, ≥75 to <85, ≥85 years old)
- body mass index (BMI) (kg/m^2) = $\text{Weight (kg)} / (\text{Height [cm]} / 100)^2$
- BMI category (<25 kg/m^2 , ≥25 to <30 kg/m^2 , ≥30 kg/m^2)
- the duration of AD from diagnosis (years) = $([\text{Date of informed consent} - \text{Date of AD diagnosis}] + 1) / 365.25$

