- **Treatment-emergent high/low analyses:** The number and percentage of patients with treatment-emergent high and low laboratory results at any time during Treatment Period 1 will be summarized by treatment group. Planned and unplanned measurements will be included. A treatment-emergent **high** result is defined as a change from a value less than or equal to the high limit at all baseline visits to a value greater than the high limit at any time during the treatment period. A treatment-emergent **low** result is defined as a change from a value greater than or equal to the low limit at all baseline visits to a value less than the low limit at any time during the treatment period. The Fisher's exact test will be used for the treatment comparison.

For laboratory analyte measurements collected qualitatively, a listing of abnormal findings will be provided for both treatment periods combined. The listing will include but will not be limited to patient ID, treatment group, laboratory collection date, analyte name, and analyte finding.

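### Period 1 safety p-values against JAHN placebo use a non-randomised group holding only placebo responders and partial responders, with no adjustment for responder status

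*SAP*

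**What the plan says.** **Planned safety tests.** For adverse events, study drug discontinuation and other categorical safety outcomes, SAP Section 6.2.3 specifies a Fisher procedure that "will be used to test for differences between each baricitinib dose (including those that are randomized to a different dose) and placebo in proportions". Continuous safety variables use "an ANCOVA with treatment group and baseline value in the model", reporting the "p-value associated with the LSM comparison to placebo or appropriate comparator". Section 6.14.3 adds between-treatment ANCOVA p-values under the laboratory box plots. For treatment-emergent high and low laboratory results in Period 1 it says: "The Fisher's exact test will be used for the treatment comparison". Section 6.14.4 extends the laboratory methods to vital signs. The general rule in Section 6.2 is: "Statistical tests of treatment effects and confidence intervals (CIs) will be performed at a 2-sided significance level of 0.05, unless otherwise stated".

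**Who is on placebo in JAHN.** Under Section 5.2, patients from the originating placebo arms (and the lower-dose baricitinib arms) who are "classified as nonresponders, will be randomized in a 1:1 ratio to 2-mg baricitinib or 4-mg baricitinib". For the rest: "All other patients will be assigned to treatment in Study JAHN matching their prior assignment from Studies JAHL, JAHM, or JAIY". Section 5.1 defines a nonresponder as any patient who is not an unrescued IGA 0 or 1 (responder) or an unrescued IGA 2 (partial responder).

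**Efficacy.** Section 6.2.3 says that "no formal comparisons between treatment groups and placebo will be conducted for the responder and partial responder mITT populations", because few placebo patients are expected to be responders. For nonresponders it lists only contrasts between baricitinib doses.

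**The concern.** A safety p-value against placebo is normally read as evidence about the drug, because randomisation makes the groups comparable. Here placebo membership depends on having done well on placebo in the originating study. The groups tested against it include, or consist entirely of, patients who did not do well on their assigned treatment. Disease severity, topical corticosteroid use and infection risk may plausibly differ between such groups whatever the drug does. A difference in adverse events, laboratory values or vital signs could then appear, or a real one could be masked, through case mix alone. A baseline laboratory or vital-sign covariate does not stand in for responder status, and the Fisher tests have no covariate at all.

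**Working it through.** **Step 1. Trace the assignment rules into the safety groups.**

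- Period 1 placebo group (Table JAHN.6.1): patients on placebo at JAHN entry. By Section 5.2 no placebo nonresponder remains on placebo, so only unrescued IGA 0-2 patients can be in it. Table JAHN.6.3 agrees: placebo-to-placebo appears only under responders and partial responders.
- Dose-switch groups (Table JAHN.6.1: placebo or 1 mg to 2 mg; placebo, 1 mg or 2 mg to 4 mg): only nonresponders are randomised to a new dose at entry, so these groups are wholly nonresponders. The Fisher sentence in Section 6.2.3 names groups randomised to a different dose as test arms.
- Same-dose 2 mg and 4 mg groups: a mixture of responders, partial responders and nonresponders. Open-label addendum patients, who entered with IGA 3 or more (protocol addendum Section 4.5.1), are pooled into 2 mg (SAP APP.1.2.15).
- The placebo group in the combined Period 1 and 2 box plots is again defined by placebo at JAHN entry.

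**Step 2. Look for an adjustment.** Neither Section 6.2.3 nor Section 6.14.3 includes responder status or originating study in a safety model or stratifies a safety test by it.

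**Step 3. Illustrate the size.** The plan has no figure to reproduce: it gives no placebo group size, no event rates and no power for this comparison. All inputs below except alpha are assumptions.

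- Alpha 0.05, two-sided (Section 6.2).
- No drug effect; incidence depends only on responder status.
- 500 baricitinib patients; placebo n from 20 to 150.
- Incidence 50% in responders and partial responders, hence 50% on placebo.
- Baricitinib group 80% nonresponders. With 60% incidence in nonresponders: 0.8 × 60% + 0.2 × 50% = 58%. With 55%: 0.8 × 55% + 0.2 × 50% = 54%. A dose-switch group, all nonresponders at 60%: 60%.

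The rejection probability is the sum, over all pairs (x0, x1) whose two-sided Fisher p-value is at most 0.05, of Bin(x0; n0, p0) × Bin(x1; 500, p1), by exact enumeration.

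| Baricitinib v placebo incidence | n0=20 | 30 | 50 | 100 | 150 |
|---|---|---|---|---|---|
| 50% v 50% (same case mix) | 3.9% | 3.8% | 3.7% | 4.8% | 4.1% |
| 54% v 50% | 5.2% | 5.7% | 6.5% | 10.8% | 12.7% |
| 58% v 50% | 9.0% | 11.3% | 16.7% | 29.8% | 40.3% |
| 60% v 50% (all nonresponders) | 12.0% | 15.8% | 25.7% | 43.5% | 57.6% |

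The first row confirms that the test holds its level when case mix is equal; the excess in the other rows is due to case mix.

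**Step 4. Rarer events.** With 300 baricitinib patients and assumed incidences of 2% in responders and 6% in nonresponders, rejection at placebo n=30, 60 and 100 is 0.3%, 0.8% and 8.2% if half the baricitinib group are nonresponders, and 0.0%, 10.6% and 27.5% if all are. Inflation is therefore not universal. With a small placebo group the test may simply be uninformative: for a true 10% v 20% with no case-mix difference, power at the same three sizes is 19%, 44% and 64%.

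**The case against.** Several limits on this point are sound.

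- **Reach.** The Fisher sentence directly follows text on the US submission lock. For the February 2021 and final locks, Section 6.14 restricts JAHN-alone safety to disposition and four kinds of adverse event table, and Sections 6.14.2 to 6.14.2.3 name no test for those tables. At the final lock they use the Period 2 groups (Section 6.2.1), which contain no carried-over placebo group. This stands. However, the Period 1 adverse event tables for February 2021 still show placebo, and Version 8 keeps the testing language in Sections 6.2.3 and 6.14.3 without withdrawing or confining it.
- **Comparator.** Only the Fisher sentence in Section 6.2.3 is tied to placebo. The ANCOVA wording permits placebo or another suitable comparator, and Section 6.14.3 does not name one. These passages therefore allow the comparison without requiring it.
- **Consequence.** Section 6.14 says safety is assessed more thoroughly in data combined with the originating studies, and Section 6.1 claims no powered comparison. This lessens the consequence but does not make the JAHN-alone p-values interpretable as drug effects.
- **Illustrative inputs.** The larger rejection rates need a placebo group of 100 or more, which sits uneasily with the SAP's own expectation of few placebo responders.

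Three stronger readings are tempting and should be resisted. A reader might infer that the SAP itself rejects the placebo comparison for efficacy as confounded. Its stated reason is small numbers, and Section 6.11.1 still mentions logistic regression comparisons in that same population. What does carry over is that the group judged too small for formal efficacy comparison is the same comparator used for safety. A reader might also say the tests have no valid null. Equality of proportions is a well-defined null; what fails is attributing a rejection to the drug. Finally, a reader might extend the criticism to Period 2. Placebo in the substudy is rerandomised 1:1:1 within prior dose (Section 5.2), so that comparator is not selected in this way.

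**Conclusion.** The point holds for Period 1 and for the combined Period 1 and 2 box plots. That the placebo safety group is confined to responders and partial responders follows from the SAP's own rules and needs no assumption. That a p-value against it can reflect case mix follows from the lack of randomisation and of any adjustment for responder status. The inference about confounding is ours; the SAP does not state it.

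The size is uncertain because it rests on assumed event rates, nonresponder share and group sizes. With no drug effect and 500 baricitinib patients, false rejection is about 9-11% at placebo n=20-30 and 17-40% at n=50-150 for 58% v 50%. For 54% v 50% it is 5-13% over n=20-150. The low end is the more relevant if placebo numbers are as few as the SAP expects. The change is worth making because it is cheap and prevents misreading, but it does not undermine the final-lock adverse event tables or the integrated safety assessment.

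**What to change.** In SAP Sections 6.2.3 and 6.14.3 (and so in Section 6.14.4, which adopts the laboratory methods), remove formal tests and p-values against the carried-over JAHN Period 1 placebo group, including in the combined-period box plots. Present that group descriptively, and state that it consists of unrescued placebo responders and partial responders and is not a randomised comparator. Label any comparison against it already reported from an earlier lock as non-randomised.

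Do not replace these tests with new safety tests on the contrasts listed in Section 6.2.3. Those are efficacy contrasts. Table JAHN.6.1 pools originating arms and does not define nonresponder groups by arm. In Period 2 the placebo and lower-dose arms are censored at retreatment while the stay-on-dose arms are not, so simple proportion tests there would compare unequal follow-up.

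The cost is a wording change, some relabelling, and fewer p-values in the safety tables.

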5.1. Summary of Study Design

Study JAHN is a Phase 3, multicenter, double-blind study to evaluate the long-term safety and efficacy of daily baricitinib 1 mg, 2 mg, and 4 mg in patients with atopic dermatitis (AD) for approximately 2 years. The study will consist of 3 study periods and 1 substudy: randomized treatment withdrawal and downtitration. Patients entering Study JAHN will be classified as “responders,” “partial responders” or “nonresponders” based on the following criteria:

- **Responders (IGA of 0 or 1):** patients entering Study JAHN who have an IGA score of 0 or 1 and were not rescued in the originating study
- **Partial Responders (IGA of 2):** patients entering Study JAHN who have an IGA score of 2 and were not rescued in the originating study
- **Nonresponders:** any patient who does not meet the “responder” or “partial responder” definitions

Figure JAHN.5.1 illustrates the study design. The full visit schedule is outlined in the Study Schedule of Activities in the Protocol. Patients who completed originating studies, such as Studies JAHL, JAHM or JAIY may be eligible for enrollment into Study JAHN. This study also includes an open-label addendum for which patients do not have to complete an originating study.

[figure not shown]
Patients completing Studies JAHL, JAHM or JAIY will have had approximately 16 weeks of treatment with investigational product (IP) (baricitinib or placebo) and will enter Study JAHN at Visit 1; the final visit of Study JAHL, JAHM or JAIY will be the first visit of Study JAHN unless washout of a concomitant medication was required in which case a new Visit 1 is required. If oral systemic AD treatments were administered for rescue in the originating study, then a minimum washout of 4 weeks is required prior to study drug initiation in Study JAHN (Visit 1). Patients will have been using emollients daily in their originating study and thus will continue during Study JAHN participation.

Daily diary dispensation/collection will continue through the first 4 months of treatment in JAHN and then dispensation will resume at Week 48 for an additional 5 months of collection to capture PROs prior to and during the withdrawal and downtitration substudy (except for patients known not to be in the substudy).

Study JAHN will consist of 4 periods:

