For patients who do not require washout, baseline will be the last visit of the originating study. Patients who received oral systemic AD treatment as rescue therapy during the originating study require a 4-week washout and will have an additional screening visit in Study JAHN (Visit 1 [Week 0]). The assessments collected at this visit will provide the Study JAHN baseline for these patients. If labs were not collected at this visit, then the most recent lab value collected at the last visit of the originating study will be used as baseline.

Period 2

For analysis of endpoints assessed at scheduled visits in Period 2, baseline from originating study will be used for categorical endpoints, such as EASI75, Itch NRS ≥ 4 -point improvement response, etc. Baseline from originating study will also be used for EASI-related, continuous endpoints, such as EASI change or percent change from baseline. For the other continuous endpoints such as Itch NRS and DLQI change from baseline, the analysis will be done using the Week 52 baseline. The methodology for defining Week 52 as the baseline is the same as the methodology for defining Week 0 of the originating study described above, anchoring on the first study drug administration of Period 2.

Safety Analyses

Safety analyses for treatment Period 1, and for Treatment Periods 1 and 2 combined (box plots of laboratory analytes and vital signs) will be conducted using the Study JAHN baseline, which is defined as the last nonmissing scheduled (planned) measurement on or prior to the date of first study drug administration for continuous measures by-visit analyses and non-missing measurements on or prior to the date of first study drug administration in Study JAHN for all other analyses. Safety analyses for Treatment Period 2 will be conducted for AEs only. Baseline for Treatment Period 2 is defined as nonmissing measurements on or prior to the date of first study drug administration in Treatment Period 2 of Study JAHN.

Postbaseline

Period 1(Weeks 0 to 52)

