6.3. Adjustments for Covariates

The randomization to treatment groups in the originating studies is stratified by disease severity (IGA) and geographic region. For Period 1, the covariates used in the logistic model for categorical data will include the baseline value from the originating study. When an MMRM analysis is performed, baseline value from originating study and baseline-by-visit interactions will be included as covariates. Unless otherwise specified, the statistical analysis models will adjust for these stratification variables. For Period 2, the covariates used in the logistic model for categorical data will include the baseline value from Week 52.

The baseline value from Study JAHN will be used as a covariate in the ANCOVA model for continuous safety data.

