6.14.3. Clinical Laboratory Evaluation

For the categorical laboratory analyses (shift and treatment emergent), the analysis period is defined as the treatment period plus up to 30 days off-drug follow-up time. The analysis period for the continuous laboratory analyses (eg, change from baseline by time point) is defined as the treatment period excluding off-drug follow-up time.

All laboratory tests will be presented using the International System (SI) and US conventional (CN) units. The performing central laboratory reference ranges will be used to define the low and high limits.

There is one special circumstance for laboratory values to be derived based on regularly scheduled, protocol-specified analytes. The low-density lipoprotein/high-density lipoprotein (LDL/HDL) ratio will be derived as the ratio of LDL cholesterol to HDL cholesterol. There are no central lab reference ranges for the LDL/HDL ratio.

The following will be conducted for the laboratory analytes collected quantitatively:

- **Box plots:** Values at each visit (starting at first visit in Study JAHN) and change from last baseline to each visit and to last postbaseline measure will be displayed in box plots for patients who have both a baseline and at least 1 postbaseline visit. The last nonmissing observation in the treatment period will be used as the last observation. Box plots will be provided for Treatment Period 1 and for Treatment Periods 1 and 2 combined. Individual measurements outside of reference limits will also be displayed using distinct symbols overlaying the box plot. Original-scale data will be used for the display but for some analytes (eg, immunoglobulins) a logarithmic scale may be used to aid in viewing the measures of central tendency and dispersion. Unplanned measurements will be excluded. Descriptive summary statistics will be included below the box plot along with p-values resulting from between-treatment comparison in change from last baseline to last observation. An ANCOVA model with explanatory term for treatment and the baseline value as a covariate will be used. These box plots will be used to evaluate trends over time and to assess a potential impact of outliers on central tendency summaries.

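### The within-group safety p-value tests an LS-mean change at the overall baseline, not the group's own change, so it can mislead where JAHN baselines differ (minor correction)

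*SAP*

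**What the plan says.** SAP Section 6.2.3 covers vital signs, body weight, laboratory and other continuous safety variables. They "will be analyzed by an ANCOVA with treatment group and baseline value in the model". On change within a group it says: "The significance of within-treatment-group changes from baseline will be evaluated by testing whether or not the treatment group LSM changes from baseline are different" (null: zero). It adds that "the within-group p-value for the change from baseline will be displayed", next to the LS means. No paired or one-sample test of a group's own change is specified, and the baseline value at which the LS means are evaluated is not stated.

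Section 6.3 fixes the covariate: "The baseline value from Study JAHN will be used as a covariate in the ANCOVA model for continuous safety data". Section 6.2.2 says the Period 1 and combined-period safety analyses "will be conducted using the Study JAHN baseline, which is defined as the last nonmissing scheduled (planned) measurement" up to first dose in JAHN for by-visit continuous measures. Section 6.14.3 repeats the model for laboratory box plots ("An ANCOVA model with explanatory term for treatment and the baseline value as a covariate will be used"), and Section 6.14.4 carries it over to vital signs and physical characteristics.

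Four places describe who is in the groups:
- Section 5.1: rollover patients arrive after about 16 weeks on baricitinib or placebo.
- Section 5.2: only nonresponders who were not on 4 mg are randomised at JAHN entry. All others keep their previous arm.
- Table JAHN.6.1: the safety groups are defined by previous and current dose.
- Appendix 1, APP.1.2.15: open-label patients, who have no originating study, are pooled into the 2-mg group.

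**The concern.** The question asked is whether a safety measure changed within a treatment group, so the null should be that the group's mean change is zero. The planned test addresses a different null: that the change would be zero in a version of the group re-centred at the baseline mean of everybody in the model.

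In a trial with one randomisation the two nulls differ only by chance imbalance. Here a systematic difference is plausible. For a measure that baricitinib moves in the first 16 weeks, the continuing 4-mg group starts JAHN already shifted. Placebo patients and open-label starters do not, and groups that switched dose contain a mixture. If that measure then stays level, the continuing 4-mg group has a true JAHN change of zero, yet its LS-mean change is pushed away from zero in the direction of the early shift. A reader could take the p-value as evidence of a further rise on long-term treatment. In groups with lower baselines the push is the other way, and a real rise is somewhat understated.

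**Working it through.** The documents give no error rate, SD or group size for this test, so there is no planned figure to reproduce.

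**Inputs from the documents.** The model has treatment group and JAHN baseline, with no interaction (6.2.3, 6.3, 6.14.3). The level is two-sided 0.05 (6.2). Group composition is as in 5.1, 5.2, Table JAHN.6.1 and APP.1.2.15.

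**Assumed inputs.** Baseline and follow-up have unit variance and within-patient correlation ρ. Every group has true mean change 0. The JAHN baseline of the continuing 4-mg group is shifted by d SD from untreated patients. Six illustrative groups:

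| Group | n | Baseline shift |
|---|---|---|
| Placebo | 60 | 0 |
| 1 mg | 60 | d/4 |
| Switched to 2 mg | 300 | d/16 |
| 2 mg incl. open-label | 400 | 0.2d |
| Switched to 4 mg | 350 | d/8 |
| Continuing 4 mg | 250 | d |

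**Step 1: what the LS mean is.** With a common slope s of follow-up on baseline, least squares gives

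LSM change = own mean change + (1 - s) x (own baseline mean - overall baseline mean).

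With stable variance s = ρ. The last term vanishes only if the group's baseline mean equals the overall mean, or if s = 1.

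**Step 2: distance from the overall baseline.** The overall shift is d x (0 + 15 + 18.75 + 80 + 43.75 + 250)/1420 = d x 407.5/1420 = 0.287d. Continuing 4 mg therefore lies 0.713d above the overall mean. For d = 0.3 that is 0.214 SD. At ρ = 0.5 the expected LSM change is 0.5 x 0.214 = 0.107 SD although the true change is 0. Simulation also gives 0.107.

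**Step 3: rejection rate.** The standard error is about sqrt((1 - ρ²)/n), so the noncentrality is 0.713d x sqrt(n) x sqrt((1 - ρ)/(1 + ρ)). For d = 0.3, n = 250, ρ = 0.5 this is 0.214 x 15.81 x 0.577 = 1.95, and Φ(1.95 - 1.96) is about 50%. The same formula gives, for continuing 4 mg:

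| d | ρ = 0.5 | ρ = 0.7 | ρ = 0.8 | ρ = 0.9 |
|---|---|---|---|---|
| 0.1 | 10% | 8% | 7% | 6% |
| 0.2 | 26% | 16% | 12% | 8% |
| 0.3 | 50% | 30% | 20% | 12% |
| 0.5 | 90% | 66% | 47% | 25% |

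Simulation of the fitted ANCOVA agrees: 49%, 30% and 19% at d = 0.3 for ρ = 0.5, 0.7 and 0.8, about 12% at ρ = 0.9, and about 5-13% across ρ at d = 0.1. A paired t-test on the same data rejects about 4-6%.

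**Step 4: the other groups.** At d = 0.3 the placebo group lies 0.086 SD below the overall mean, so its LSM change is biased by -(1 - ρ) x 0.086: -0.04 SD at ρ = 0.5 and -0.01 SD at ρ = 0.9. At ρ = 0.7 the five other groups reject in only about 5-8% of trials.

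**Step 5: between-group differences.** Subtracting two LS means cancels the overall baseline mean, because the model has no interaction. The planned contrasts do not depend on where the LS means are evaluated.

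**The case against.** The strongest reply concerns reach. The 6.2.3 paragraph opens with the US submission lock. For the February 2021 and final locks, Section 6.14 restricts safety to disposition and four adverse-event tables and sends other detailed safety assessments to an integrated plan. Section 6.14.3 mentions p-values only for between-treatment comparisons, and it already displays observed change by visit with descriptive statistics, where a flat 4-mg group would look flat. The study is unpowered and no decision is tied to this p-value. The SAP also says openly that it tests the LS-mean change. All of this stands, and it is why the point is minor. It does not remove the problem: 6.2.3 still contains the test, it is the only within-group test specified, and its sentence on continuous safety variables is not expressly confined to one lock.

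The size also depends on the inputs. Correlation may be high for weight and BMI, and a small baseline shift leaves the test near nominal.

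A reader might infer more than the documents support:
- That inflation is at least twofold in every plausible case. It is not: a 0.1 SD shift at correlation 0.9 gives about 6%.
- That comparisons between treatment groups are biased by the same mechanism. They are not (Step 5).
- That real rises are substantially hidden in patients who start or switch up. The bias there is about -0.01 to -0.04 SD at a 0.3 SD shift.
- That ANCOVA should be confined to groups randomised to each other. That is a separate question and does not follow from this one.

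**Conclusion.** The point holds as a minor, low-priority correction. The mismatch between the stated question and the planned test is exact algebra, given the usual convention that LS means are taken at the overall covariate mean. The SAP neither states nor overrides that convention.

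The size is conditional on assumed baseline shifts, correlations and group sizes. For continuing 4 mg with no true change, false flags run at about 19-49% for a 0.3 SD shift with correlation 0.8-0.5, and approach the nominal 5% as the shift shrinks or the correlation rises. The effect falls mainly on that one group.

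The reach is the Period 1 and combined-period laboratory, vital-sign and weight analyses, such as those for the US lock. The February 2021 and final locks are outside it, so the documents do not support a claim that the final analysis is compromised.

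**What to change.** In Section 6.2.3, replace the within-group LS-mean test and its displayed p-value with: *Within-group change will be summarised by the observed mean change with its standard error and 95% CI, and tested by a paired t-test within each treatment group.* Keep the ANCOVA for the between-group differences as planned. If LS means by group are still shown, state the baseline value at which they are evaluated.

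Do not instead evaluate each LS mean at the group's own baseline and use the model standard error. The estimate is then the raw mean change, but the standard error is too small: rejection was 5.3% to 9.3% in one set of simulations and up to about 10% in another, against a nominal 5%.

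The cost is one sentence of SAP text and a small programming change, with no new data. The downside is a slightly larger within-group standard error, because the covariate adjustment is given up.
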